Prior to catheter placement the physician will perform a modified Allen's Test to confirm adequacy of collateral circulation of the hand. A physician ([name]) will perform catheterization of the radial artery. Using a standard, sterile procedure [name] will place a small catheter into the radial artery (arterial catheterization). [name] will initially numb the wrist with lidocaine/nitroglycerin solution. Then [name] will place a needle into the radial artery. [name] will then place a small guide wire through the needle in to the vessel. Then he will place a flexible catheter into the vessel using the guide wire for direction. This catheter will be used to collect blood totaling <100 mL (< 7 Tablespoons) in the exercising subjects and < 25 ml (<2 Tablespoons) in resting subjects. Blood draws will be accompanied by a heparinized saline flush (1unit heparin/ml) to reduce chances of catheter clotting. 12 lead ECG, heart rate, metabolic, ventilation data will be continuously collected and arterial blood oxygen saturation will be continuously measured via a non-invasive transcutaneous forehead sensor.

*Note:

TOTAL blood draw for Exercise subjects (i.e., IV + Arterial Line) will be less than 250 mL. TOTAL blood draw for Non-Exercise subjects (i.e., IV + Arterial Line) will be less than 125 mL.

However, if it is deemed at 6 months by the referring physician that the PFO/ASD has not been physically closed/endothelialized, subjects will not partake in the scheduled 6-month post PFO/ASD closure procedure visits. Thus, the amount of blood drawn from these subjects would be significantly reduced. Specifically:

Exercise subjects without 6 month visits (i.e., total blood drawn): < 125 mL Non-exercise subjects without 6 month visits (i.e., total blood drawn): < 75 mL Risks and interventions to mitigate such are included in Section G.

• Exercise with arterial line (Days 3, 6a OR 7b Exercise subjects only):

After arterial line placement (see above) the subjects will perform two bouts of graded submaximal exercise tests on the cycle ergometer at 25%, 50%, 75% and 90% of their VO_{2max} with each stage lasting 4 minutes with up to 15 minute breaks between stages. During one bout, subjects will breathe normal oxygen levels (21% oxygen), during the other bout, subjects will breathe high oxygen levels (40% oxygen). Bouts will be randomized and separated by 30 minutes of rest breathing room air.

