• Intrapulmonary & intracardiac Shunting with arterial line placement (Days 3, 6a OR 7b Exercise subjects; Days 2-3a OR 4b NON-Exercise subjects):

Saline contrast echocardiography will be performed during the third minute of each exercise stage to assess intrapulmonary and intracardiac shunting. Saline contrast echocardiography will also be performed in NON-exercise subjects at rest.

 Measurement of core body temperature (Days 3, 6a OR 7b Exercise subjects; Days 2-3a OR 4b NON-Exercise subjects):

An esophageal temperature probe (Nelcor used with Mon-a-Therm System) will be placed. We will be using esophageal temperature monitoring because core temperature is a primary outcome variable of this study and esophageal temperature is considered to be the gold standard technique for measuring core temperature during short duration exercise testing. We also use this temperature to correct our blood gas values. In order to place the esophageal probe, subjects will be given lidocaine Jelly (2% lidocaine, 1 ml intranasal administration). After administration of the lidocaine Jelly, researchers will place the esophageal probe through one of the nostrils, and advance the probe until it is visible in the back of the throat. Once the probe is visible, the subject will then begin to sip water through a straw while the researcher advances the probe to the appropriate depth. The swallowing of the water helps to insure that the probe goes down the esophagus and not the trachea. Researchers will make no more than 2 attempts per nostril to place the esophageal probe. In the event subjects cannot tolerate the esophageal temperature probe, subjects will swallow an ingestible pill, about the size of a multi-vitamin, that is designed for human use (FDA approved) and is accurate to 0.1°C (CoreTemp, HQI Technologies, Inc.). This pill will be used to measure core body temperature at rest and during cycle ergometer exercise. Prior to ingestion the temperature pill will be calibrated with an external wireless recording device. This will allow us to wirelessly acquire the subjects core temperature when necessary as the temperature pill transmits a signal to the external device that will then display the appropriate temperature. This pill will harmlessly pass through the subject's intestinal tract. The pill is not recovered, is disposable, and every subject receives a new pill for each study day.

Table 1 – Exercise

Group - Exercise											

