D. Research Population & Recruitment Methods & Compensation

1-2. Sample size, Population and Recruitment Methods:

Sample Size and Data Analyses:

Necessary sample size was determined with our primary outcome variables ($AaDO_2$, VO_{2MAX} , saline contrast bubble scores, TNFa levels) using our preliminary data, previously published work and *a priori* power analysis. Using G-Power and information about a physiologically-meaningful effect from published studies (i.e. reduction of $AaDO_2$ by 50%, VO_{2MAX} increasing by 10% and 6 min walk test increasing by 50 meters (15, 34, 41)(24, 40)(24, 40), TNF-a levels decreasing by 50%, a desired power of 0.80, and alpha (0.05), we determined that n = 8-10 individuals would be sufficient to test our hypotheses, using a repeated measures design. Thus, we are asking to recruit 20 subjects (any combination of male and female) in the event

our actual pre-to-post changes are less than expected and/or there is greater variability than our preliminary data suggest.

Mean differences in $AaDO_2$ and core body temperature between pre- and post-PFO/ASD closure will be analyzed using a repeated measures ANOVA with Tukey posttest. Mean differences in $VO_{2MAX,}$ 6 minute walk test, activity, inflammatory markers and hypercapnic ventilator response, between pre and post PFO/ASD closure will be analyzed using a paired t-test. Differences in bubble scores pre- and post-closure will be analyzed using a Mann-Whitney U test.

The population of subjects will include patients who are undergoing PFO/ASD closure at either PeaceHealth or McKenzie-Willamette Hospitals. Subjects will be identified by [name] (PeaceHealth/Oregon Heart & Vascular Institute) and [name] (McKenzie-Willamette). These two cardiologists will only refer subjects to contact the [name] Lab for informed consent and enrollment into the study. Drs. [name] and [name] will identify potential subjects as "cleared for exercise" or "not cleared for exercise." (See statement of PHI above). Drs. [name] and [name] will not be formally engaged in the research (i.e. they will not consent subjects, have access to identifiable data, etc). No research activities will take place at either hospital. Subject fliers, initial phone script and email script are attached.

3. Detailed Recruitment information:

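### The repeated measures ANOVA for AaDO2 and core temperature has no stated factors; if exercise stage is one of them, a classical ANOVA omits all rest-only subjects and any exercise subject with one missing cell

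*Combined protocol and SAP*

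**What the plan says.** Section D assigns a paired t-test to VO2max, six-minute walk, activity, inflammatory markers and hypercapnic response. It treats two outcomes differently: mean differences in AaDO2 and "core body temperature between pre- and post-PFO/ASD closure will be analyzed using a repeated measures ANOVA with Tukey posttest". It does not give the factors of that ANOVA, say whether the exercise and non-exercise groups are pooled, or say what happens to incomplete subjects.

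The data behind these outcomes differ by group:

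- Exercise subjects cycle "at 25%, 50%, 75% and 90% of their VO_{2max} with each stage lasting 4 minutes", once on 21% and once on 40% oxygen, before and after closure (section C, Exercise with arterial line). They also have resting arterial samples.
- Non-exercise subjects have arterial blood and core temperature at rest only, before and after closure (section C, non-exercise visit descriptions, and Table 2). The same holds for their shunt imaging: "Saline contrast echocardiography will also be performed in NON-exercise subjects at rest".

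Resting arterial blood is drawn on room air and on 100% oxygen, the latter for shunt fraction. The exercise visit descriptions in section C add that 60% oxygen is the highest level that still yields the metabolic data needed for AaDO2.

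On size, section D specifies "a desired power of 0.80" at alpha 0.05 and concludes that "n = 8-10 individuals would be sufficient to test our hypotheses, using a repeated measures design". It asks for 20 subjects in case changes are smaller or more variable than expected. It plans no split between the groups and makes no allowance for incomplete data.

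**The concern.** A Tukey posttest adds nothing to a comparison of two levels, before and after. Its presence, the paired t-tests assigned to the other continuous outcomes, and Aim 1 (AaDO2 at rest and in exercise) together make a stage factor the natural reading. A classical repeated measures ANOVA needs every cell filled for every subject it uses. It would therefore have no place for the rest-only subjects, and one missed stage or one lost arterial sample would remove all of an exercise subject's data.

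AaDO2 is a primary outcome in section D, and the core temperature paragraph of section C calls core temperature one as well. At stake are paired data collected through arterial lines and then not used, a smaller analysed sample in a study of 20, and an estimate drawn from a selected subset.

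**Working it through.** **The plan's own figure.** The required n of 8-10 cannot be reproduced, because no baseline mean, SD of change or within-subject correlation is given. Working back with a two-sided paired t-test at alpha 0.05 (noncentral t; sidedness assumed), power 0.80 requires a standardised change dz of 1.16 at n = 8 or 1.00 at n = 10. For a 50% fall in AaDO2 this implies an SD of change of 50/1.16 = 43% to 50/1.00 = 50% of the baseline mean.

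**Cells per exercise subject.** 4 stages x 2 gases x 2 visits = 16 exercise cells. The hardest stage, 90% of VO2max, accounts for 1 x 2 x 2 = 4 of them.

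**Share of exercise subjects complete.** Let p be the probability of missing a 90% cell, independent across the four cells, with nothing else missing. Both p and independence are assumptions. The share complete is (1 - p)^4:

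- p = 0.05: 0.95^4 = 0.815
- p = 0.10: 0.90^4 = 0.656
- p = 0.15: 0.85^4 = 0.522

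Independence is pessimistic here, because a person who fails once is likely to fail again. With an assumed latent correlation of 0.8 between the four cells, the shares are 0.89, 0.81 and 0.73. In the other direction, if any of the 16 cells can be lost, 5% per cell leaves 0.95^16 = 0.44.

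**Expected number analysed** (independent case; the number of exercise subjects among the 20 is assumed):

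| Exercise subjects | p = 0.05 | p = 0.10 | p = 0.15 |
|---|---|---|---|
| 20 | 16.3 | 13.1 | 10.4 |
| 12 | 9.8 | 7.9 | 6.3 |
| 10 | 8.1 | 6.6 | 5.2 |

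**Power.** At dz = 1.0, power is 0.80 at n = 10, 0.68 at 8, 0.60 at 7 and 0.51 at 6. At dz = 1.16, the value implied by n = 8, power is 0.80 at 8 and 0.62 at 6.

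**Direction of bias.** Let the true mean change be 1.0 SD, drop a fraction q of subjects, and let r be the correlation between the tendency to be dropped and the benefit. Under normality the complete-case mean is 1 - r x phi(z)/(1 - q), where z is the 1 - q quantile and phi the standard normal density. For q = 0.25, phi(z)/(1 - q) = 0.318/0.75 = 0.424, so the mean is 0.79 at r = +0.5, 1.00 at r = 0 and 1.21 at r = -0.5. For q = 0.50 the values are 0.60, 1.00 and 1.40. The sign of r decides the direction, and the documents give no information on r.

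**Are gas and condition crossed?** No. AaDO2 conditions that can be used are rest on room air and each stage on 21% and on 40%: 1 + 4 x 2 = 9 conditions, or 18 cells over two visits. The section describes no resting sample on 40%, and resting 100% oxygen lies above the 60% limit stated for AaDO2. A rest-plus-stages by gas layout would be incomplete even for a subject who finished everything.

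**The case against.** The strongest reply is that the loss depends on a model the plan never states. Section D refers only to differences before and after closure, and section D.3 speaks of separate exercise and non-exercise arms. A resting analysis of everyone, with a separate exercise analysis, would keep the rest-only subjects. Non-exercise subjects have no exercise AaDO2 by design, so their absence from an exercise contrast loses nothing. This stands, and it makes the finding conditional. It does not resolve it, because the plan specifies neither of those analyses, and separate analyses would still need a rule for missed stages.

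The second reply is that the loss may be modest. Take an illustrative simulation with 12 exercise and 8 rest-only subjects, about 15% failing the 90% stage before closure and 6% after, and both failure and benefit rising with severity. The ANOVA kept 9.7 of 20 on average, which is within 8-10. Of the 10.3 lost, 8 were rest-only by construction, so about 2.3 of 12 exercise subjects went. The estimates were -5.16 mm Hg (ANOVA) and -5.60 (mixed model) against a true -5.76. This also stands: the power figures for n = 6 to 8 are possible outcomes, not expected ones.

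A reader might infer more: that those dropped are the sickest, so the ANOVA understates the benefit. The documents do not support this. In the simulation just described, the shrinkage follows from the assumed link between severity and benefit. The only example of a patient not cleared for exercise (section D.3) is chest pain with an ECG abnormality, not shunt size or gas exchange. Stages are set relative to each subject's own VO2max, with rest breaks, so nothing shows that worse AaDO2 means failing the 90% stage.

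**Conclusion.** The concern holds in conditional form. The model for two outcomes that the plan calls primary is unspecified. On its most natural reading it does not fit a design in which the two groups fill different cells. A classical ANOVA with a stage factor would omit all rest-only subjects and each exercise subject with any gap.

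Under assumed independent miss rates of 5% to 15% per 90% cell, 81% to 52% of exercise subjects remain; with strongly clustered failures, 89% to 73%. Whether the analysed number falls below 8-10 depends on the unplanned split: not at these rates if all 20 exercise, but readily if 10 to 12 do. Bias is possible and its direction is unknown. The miss rates, the split and dz are assumptions, not figures from the plan. Missed stages are nonetheless foreseeable: the 90% stage is attempted twice at each of two visits, by patients aged up to 80, some with exercise-induced hypoxaemia.

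**What to change.** In section D, replace the repeated measures ANOVA for AaDO2 and core temperature with a linear mixed model (REML, small-sample degrees of freedom) on all available measurements:

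- Fixed effects: visit (before/after closure), condition, and visit-by-condition. Code condition as the combinations actually measured: rest on room air, and each stage on 21% and on 40% oxygen. Do not enter gas as a separate crossed factor.
- Random effects: subject intercept and subject-specific visit effect.
- Keep the resting 100% oxygen samples for shunt fraction and out of the AaDO2 model.
- Estimate the resting before/after contrast from both groups and the exercise contrasts from exercise subjects.
- Report how many subjects missed each stage at each visit.

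Separate resting and exercise analyses with a written missing-data rule would also remove the ambiguity, but would use the data less fully.

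The cost is a change of analysis wording. The data and visits stay the same and standard software suffices. The downside is slightly more modelling work and reliance on a missing-at-random assumption in a small sample; the mixed model would not remove bias from stages missed for reasons unrelated to anything observed but related to the missing value.

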Lastly, preliminary data also suggest greater levels of plasma inflammatory mediators in subjects with a PFO and systemic inflammation is associated with increased risk of cardiovascular diseases. Importantly, exercise is known to reduce so of these systemic inflammatory mediator levels. Thus, PFO/ASD closure may allow for greater exercise capacity and a subsequent reduction in inflammation.

Thus, although a PFO has been traditionally considered to have a minimal impact of physiology and pathophysiology, emerging evidence suggests this may not be the case. Our lab is focused on understanding how and why a relatively small hole in the heart (PFO/ASD) can have a relatively large impact on cardiopulmonary and respiratory physiology.

B. Specific Aims/Study Objectives

The overarching goal of this study is to examine cardiopulmonary and respiratory physiology pre and post PFO/ASD closure in patients who are undergoing surgical closure of their PFO/ASD.

Pre and post PFO/ASD closure, we will:

- 1) Quantify pulmonary gas exchange efficiency (alveolar to arterial O2 difference) and arterial oxygenation at rest and during exercise.
- 2) Quantify aerobic exercise capacity, daily activity, six-minute walk test.
- **3**) Quantify Q_{IPAVA} at rest and assess recurrence of stroke or TIA at 3 months.
- **4)** Quantify plasma inflammatory markers (TNFa, IL-1, 6 & CRP)
- **5)** Measure hypercapnic ventilatory response
- **6)** Quantify core body temperature

Hypotheses: We hypothesize that closure of PFO/ASD will improve pulmonary gas exchange efficiency, improve exercise capacity, and reduce blood flow through PFO/ASD and IPAVA thereby preventing subsequent stroke. PFO/ASD closure will also reduce plasma inflammatory mediators, increase ventilation in response to a hypercapnic challenge, and will result in a lower core body temperature.

C. Methods, Materials and Analysis

This study will be performed over the course of 7 days at the Cardiopulmonary and Respiratory Physiology Lab at the University of Oregon. Days 1-3 are Pre-PFO/ASD closure procedure and Days 4-7 repeat all research activities beginning at 3 months post PFO/ASD closure procedure. Those cleared for exercise by their cardiologists (see recruitment below)

will participate in all aspects of the study, Days 1-7. Those *not cleared for exercise* by their cardiologists will participate in all non-exercise aspects of the study Days 1-4 [gray highlight for non-exercise subject information].

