This is a standard non-invasive test for diffusion capacity for carbon monoxide (CO) using the single breath, breath-hold technique. It requires the subject to breathe in a single breath of a commercially available (MedGraphics/Airgas) diffusion gas containing 0.3% CO. The subject will breathe in this breath through a mouthpiece connected to a flowmeter and hold it for approximately 10 seconds before exhaling the gas. This may be repeated a maximum of 3 to 5 times. This is a routine clinical test performed in pulmonary function labs in the United States.

• Whole Body Plethysmography (Days 1 & 4a OR 5b Exercise; Days 1 & 3a OR 4b NON-Exercise):

Subjects perform a standard non-invasive procedure to measure functional residual capacity (FRC), which is the amount of air within the lungs at the end of a passive expiration. Subjects also perform a standard non-invasive slow vital capacity (SVC) maneuver to determine the vital capacity (usable capacity) of the lungs. These procedures will require the subject to sit inside a clear plexiglass box called a whole body plethysmograph (MedGraphics Elite) and breathe room air through a mouthpiece (pneumotachometer) connected to a flowmeter. Using the value obtained for FRC and the value obtained for SVC total lung capacity (TLC) can be determined. This is a routine clinical test performed in pulmonary function labs in the United States.

Nitrogen Washout (Days 1 & 4a OR 5b Exercise; Days 1 & 3a OR 4b NON-Exercise):

Subjects may perform a standard non-invasive procedure to measure residual volume for calculation of total lung capacity. This procedure will require subjects to breathe 100% oxygen through a mouthpiece for 7-10 minutes while we monitor nitrogen washout of the lungs. This will be done following ATS/ERS standard criteria. This is a routine clinical test performed in pulmonary function labs in the United States. This will only be performed if the plethysmograph is not functioning properly, i.e. it is a contingent test. Of note we have never needed to perform this test.

• Transthoracic Saline Contrast Echocardiography (TTSCE) (Days 1, 3, 4a OR 5b & 6a OR 7b Exercise; Days 1-3a OR 4b NON-Exercise):

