Visits:	1	2	3	4 a	4 b	5 a	5 b	6a	6 b	7 a	7b
Pre- PFO/ASD Close	Х	Х	Х								
Post-PFO/ASD Close				Х	Х	Х	Х	Х	Х	Х	х
Study Procedures:											
IC & Health Hx, HIPAA form	х										
Modified Allen Test	Х		Х					Х			Х
Comprehensive Screening	х			Х			Х				
Pulmonary Function	х			Х			Х				
Diffusing Capacity	х			Х			Х				
Plethysmography	х			Х			Х				
Nitrogen Washout*	х			Х			Х				
Transthoracic Saline Contrast Echo (TTSCE)	х		Х	х			х	Х			х
Intravenous catheter (IV)	х		Х	Х	Х		Х	Х		Х	Х
Hypercapnic Ventilatory Response		Х				Х	Х				

Actigraphy**		х		х			х				Ì
VO2Max & 6 min walk		Х		Х			Х				
Arterial Blood Gas Measurement			Х					Х			Х
Exercise w/arterial line			Х					Х			Х
Intrapulmonary/intracardiac shunt w/art line			х					х			х
Core Body Temp			Х					Х			Х
Compensation:											
IC & Health Hx	5										
Echo screen/blood draw	1 0			1 5			1 5				
Blood Draw					1 0					1 0	
PFT, diff capacity, plethysmography	1 0			1 5			1 5				
Hypercapnic breathing challenge		1 0				1 5			1 5		
activity monitor training		5									
six min walk		5				5			5		
vo2max		1 5				1 5			1 5		
arterial line			10 0					13 0			13 0
exercise tests			75				_	10 0			10 0
blood draws/breathing room air											
	2	3	17	3	1	3	3	23	3	1	23
Total for completed study visit	5	5	5	0	0	5	0	0	5	0	0
Total for all aspects of the study	540										

Table 2 – Non-Exercise

Group – Non-Exercise						
Visits:	1	2	3a	3b	4a	4b
Pre- PFO/ASD Close	Х	х				
Post-PFO/ASD Close			х	Х	Х	х
Study Procedures:						
IC & Health Hx, HIPAA form	Х					
Modified Allen Test	Х	х	х			х
Comprehensive Screening	Х		х			х
Pulmonary Function	Х		х			х
Diffusing Capacity	Х		х			х

Plethysmography	х		x			х
Nitrogen Washout*	X		X			X
Transthoracic Saline Contrast Echo (TTSCE)	X	х	x			X
Intravenous catheter (IV)	X	Х	X		х	X
Hypercapnic Ventilatory Response		x	x			х
Actigraphy**		Х	x			х
VO2Max & 6 min walk						
Arterial Blood Gas Measurement		Х	х			х
Exercise w/arterial line						
Intrapulmonary/intracardiac shunt w/art line		Х	х			х
Core Body Temp		Х	х			х
Compensation:						
IC & Health Hx	5					
	1					
Echo screen/blood draw						
Blood draw				10	10	
	1					
PFT, diff capacity, plethysmography						
Hypercapnic breathing challenge		10	15			15
activity monitor training		5				
six min walk						
vo2max						
arterial line		100	130			130
exercise tests						
blood draws/breathing room air		15	20			20
Total for completed study visit	25	130	165	10	10	165
Total for all aspects of the study	330					

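### Bubble scores, a listed primary outcome measured before and after closure in the same subjects, are assigned the unpaired Mann-Whitney U test

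*Combined protocol and SAP*

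**What the plan says.** Section B sets the goal as a within-subject comparison: to "examine cardiopulmonary and respiratory physiology pre and post PFO/ASD closure in patients who are undergoing surgical closure". Aim 3 includes "Quantify Q_{IPAVA} at rest and assess recurrence of stroke or TIA at 3 months".

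Section C schedules saline contrast echocardiography in both periods for every subject: "Transthoracic Saline Contrast Echocardiography (TTSCE) (Days 1, 3, 4a OR 5b & 6a OR 7b Exercise; Days 1-3a OR 4b NON-Exercise". Tables 1 and 2 mark the same visits. Pre-closure these are visits 1 and 3 (exercise) or 1 and 2 (non-exercise). Post-closure they are 4a or 5b and 6a or 7b (exercise), or 3a or 4b (non-exercise).

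Section D, under Sample Size and Data Analyses, begins "Necessary sample size was determined with our primary outcome variables" and lists four: AaDO2, VO2max, bubble scores and TNF-alpha. It concludes that "n = 8-10 individuals would be sufficient to test our hypotheses, using a repeated measures design", and asks to recruit 20. AaDO2 and core temperature get a repeated measures ANOVA. For VO2max, walk distance, activity, inflammatory markers and the hypercapnic response, mean differences "between pre and post PFO/ASD closure will be analyzed using a paired t-test". Then: "Differences in bubble scores pre- and post-closure will be analyzed using a Mann-Whitney U test".

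**The concern.** Mann-Whitney U treats the pre and post scores as coming from two unrelated sets of people. Here each post score has a matching pre score from the same person, and the sentence compares pre with post, not the exercise group with the non-exercise group. No independent-groups reading is available, and nowhere do the documents name a paired ordinal method.

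Two things are at stake. First, the nominal 5% level does not hold unless the pre/post correlation happens to be zero. Second, if the correlation is positive, as repeated scores in one person usually are, the pairing that the sample size counted on is discarded. Bubble scores address the second question in the study title, whether closure prevents flow through intrapulmonary shunt.

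The sentence also does not say which score it means. At rest, both flows are graded on room air and only PFO/ASD flow on 100% O2. A Valsalva maneuver and up to three injections are allowed, and exercise subjects are also scanned in every exercise stage. A within-subject difference is undefined until one condition is named.

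**Working it through.** **The plan's own figure.** Section D gives n = 8-10 for power 0.80 and alpha 0.05. It gives no standard deviation or correlation for any outcome and no effect for bubble scores, so the figure cannot be rebuilt. For a two-sided paired t-test, power is P(|T| > t(0.975, n-1)), with T noncentral t on n-1 degrees of freedom and noncentrality dz × √n. Solving for 80% power gives dz = 1.16, 1.07 and 1.00 at n = 8, 9 and 10, and 0.66 at n = 20. So 8-10 is consistent with a paired analysis of a large effect, but is not verified.

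**Why correlation matters.** With n pairs, common variance σ² and correlation ρ, the pre/post difference in means has variance 2σ²(1-ρ)/n. An unpaired test uses 2σ²/n. Ranks behave alike in large samples, so the true two-sided rejection rate under no change is about 2Φ(-1.96/√(1-ρ)). At ρ = 0 this is 5%. At ρ = 0.45 it is 2Φ(-1.96/0.742) = 2Φ(-2.64), about 0.8%. For negative ρ the divisor exceeds 1 and the rate is above 5%.

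**Simulation inputs (assumed, because the documents give none).** Bivariate normal latent scores are cut into 6 grades, either equally likely or skewed (pre-closure 35/25/20/12/6/2% from lowest to highest, as an IPAVA-type score might be). Correlation and shift are on the latent scale; latent 0.5 gives about 0.45 between grades. Tests are two-sided at 0.05. Mann-Whitney has tie and continuity corrections. Signed-rank is exact with zero differences dropped.

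Mann-Whitney rejection under no change, n = 20, equally likely grades:

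| Latent correlation | -0.3 | 0 | 0.3 | 0.5 | 0.8 |
|---|---|---|---|---|---|
| Rejection rate | 7.8% | 4.8% | 2.1% | 0.8% | under 0.1% |

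The 0.8% agrees with the formula.

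Power:

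| n | Grades | Shift (SD) | Correlation | Mann-Whitney | Signed-rank |
|---|---|---|---|---|---|
| 20 | equal | 0.5 | 0.5 | 25% | 47% |
| 20 | skewed | 0.5 | 0.5 | 23% | 38% |
| 20 | equal | 1.0 | 0 | 83% | 81% |
| 20 | equal | 1.0 | 0.5 | 89% | 96% |
| 20 | equal | 1.0 | 0.8 | 94% | 100% |
| 10 | skewed | 0.8 | 0 | about 30% | about 20% |
| 10 | skewed | 0.8 | 0.5 | 27% | 27% |
| 10 | skewed | 0.8 | 0.8 | 24% | 42% |
| 10 | skewed | 1.0 | 0.5 | 42% | 38% |
| 8 | skewed | 1.0 | 0.5 | 32% | 19% |

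At n = 20, correlation 0.3 and a 0.8 SD shift, a similar 6-level score gives 66% against 75% (signed-rank by normal approximation).

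**Signed-rank under no change.** With skewed grades and correlation 0.5, the exact test rejects about 1.2% at n = 8 and 1.6% at n = 10, against 1.1% and 1.0% for Mann-Whitney.

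**PFO/ASD-type scores.** With pre grades uniform on 1-5 and post grades 0 in 60% or 85% of subjects and 1 otherwise, both tests have power of 97% or more at n = 8-20.

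**The case against.** The best defense concerns consequence, since the mismatch itself is plain. Under positive correlation the planned test is conservative, so it would not manufacture a positive finding. Subjects whose defect is not closed at 6 months are excluded, which makes low post-closure PFO/ASD scores likely, and there the choice of test hardly matters. What is left is a loss of power for IPAVA that depends on an unstated scale, effect and correlation. The replacement is also not uniformly better. At the n of 8-10 that Section D calls sufficient, with skewed and heavily tied grades, the exact signed-rank test is itself conservative and can have less power than Mann-Whitney even at moderate correlation. All of this stands, and it lowers the severity. It does not make Mann-Whitney valid for paired data, because its error rate still turns on an unknown correlation in either direction.

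A reader might infer three stronger things that the documents do not support:
- That false positives are inflated. This needs a negative pre/post correlation, and nothing in the documents suggests one.
- That the whole bubble-score result would be lost. A fall to the floor after closure would be detected by either test.
- That a paired test always gains power. It does so at n = 20 once correlation is about 0.3 or more, but not reliably at n = 8-10.

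**Conclusion.** The test does not match the design, and the sentence should be corrected before analysis. This is a should-fix point and does not invalidate the study. The mismatch rests on the text alone. Its size is conditional on the assumed 6-level score, shifts and correlations. With those, at n = 20, the real level of the planned test runs from about 7.8% to under 1% as latent correlation goes from -0.3 to 0.5. For a 0.5 SD shift at correlation 0.5, it gives up 22 percentage points of power (47 - 25), or 15 with skewed grades (38 - 23). The loss falls mainly on the IPAVA score. The figure of 20 is the recruitment target; if appreciably fewer subjects are scored in both periods, the advantage of the paired test shrinks and may reverse.

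**What to change.** Replace the sentence in Section D with:

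> Pre- to post-closure differences in bubble scores will be analyzed with a two-sided Wilcoxon signed-rank test on within-subject differences, in subjects scored in both periods, separately for the PFO/ASD and IPAVA scores, each under one condition named in advance and the same before and after closure.

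The sponsor then needs to state, before analysis:
- The condition for each score. For IPAVA, aim 3 specifies rest, and the Section C visit descriptions grade that flow on room air. For PFO/ASD the choice is the sponsor's: 100% O2 isolates that flow, and Section C says the Valsalva maneuver enhances it.
- One rule for zero differences. Dropping them and the Pratt method differed in power by at most 1.2 points in 80 simulated settings, so either will do.
- One rule for repeat injections.
- Which of the two scores is primary, or how the two tests share alpha, since the replacement makes one comparison into two.

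The cost is a few sentences in Section D, with no new data, visits or subjects. The downside is the possible loss of power at about 8-10 subjects with tied, skewed grades: about 38% against 42% at n = 10, and 19% against 32% at n = 8, for a 1.0 SD shift at correlation 0.5.
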